## **STATISTICAL ANALYSIS**

In the descriptive study, numerical variables will be expressed as mean  $\pm$  standard deviation (SD) or median and interquartile range (IQR), depending on whether the distribution is normal or not, respectively. We will establish 2 groups of patients, according to the response to treatment and the clinical evolution of the patient with LN (i.e., complete remission yes/no). To establish differences between patients in these 2 groups, we will use the  $\chi^2$  test for categorical variables or Fisher's exact test when the expected frequencies are small, the t-Student test for normal continuous variables, and the Mann-Whitney U test for variables with non-normal distribution.

Different methods to analyze and/or mitigate the missing data problem will be used.

The percentage of positive cells and staining intensity will be correlated with the different patterns of response to treatment and evolution of LN.

Univariate and multivariate linear logistic regression analyses will be performed to explore the relationships between the different variables studied (clinical, histopathological, therapeutic...) and the presence of the different renal outcomes (dependent variable). Values of  $p < 0.05$  will be considered significant.

We will carry out other different statistical methods according to the results that we observe from our initial analysis.

Statistical analyses will be performed by the Statistical Specialist of the IRIDIS Group.

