## **INTRODUCTION**

Lupus nephritis (LN) may affect approximately half of patients with Systemic Lupus Erythematosus (SLE). LN is a major cause of morbidity and the most important predictor of mortality in patients with SLE (1,2). Some 5-20% of patients with LN may develop end-stage renal disease within 10 years of follow-up from the time of diagnosis (3). Other studies have described progression to end-stage renal disease in 10-30% of patients with LN (4,5).

The European League Against Rheumatism (EULAR), the European Renal Association (ERA) and the European Dialysis and Transplant Association (EDTA) have recently updated their recommendations for the management of LN. These recommend the use of intravenous (IV) methylprednisolone boluses followed by lower doses of oral glucocorticoids (GC) and place mycophenolate mofetil (MMF) and the European regimen of cyclophosphamide (CYC) as the immunosuppressive drugs of first choice, with the IV CYC regimen for certain more aggressive cases. They also consider the use of "multitarget therapy" based on the combination of tacrolimus (TAC) and MMF and GC in patients with proteinuria in the nephrotic range who have not responded to the first line of treatment. For refractory active renal disease, they recommend as an alternative the use of rituximab (RTX) 1000 mg IV repeated after 15 days (6).

Recently, belimumab has been shown to be significantly more effective than placebo in the treatment of patients with active LN (7). This finding will lead to positioning belimumab in the therapeutic algorithm for LN.

However, in clinical practice these immunosuppressive drugs are not always effective in the treatment of LN, and even one in 3 patients with an initial favorable response may experience renal recurrence (3).

The choice of the appropriate treatment for LN and its early initiation are key to improve the prognosis of these patients and to avoid progression to chronic renal failure.

The identification of biomarkers capable of predicting the response (or lack thereof) to one or another therapy at the time of LN diagnosis would allow to implement precision medicine, thus constituting a revolution in the treatment of patients with LN. Being able to make personalized therapeutic decisions, based on the biological characteristics of each patient's renal sample, allows more targeted treatments with greater specificity to be established.

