The **objective** of this project is to analyze histopathological biomarkers in the renal biopsy to predict the renal response to the different drugs used in the treatment of LN. This would contribute to a more specific and cost-effective therapeutic strategy.

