## **PATIENTS AND METHODS**

### **Inclusion criteria:**

Patients with a diagnosis of SLE according to the 1997 American College of Rheumatology (ACR) criteria (8).

Diagnosis of lupus nephritis type 3,4,5 or mixed forms of the above according to the International Society of Nephrology (ISN)/Renal Pathology Society (RPS) classification of LN (9).

Date of performance of the renal biopsy: year 2000 or later. The reason for this time frame is the theoretical homogenization in the therapeutic management of LN with the introduction of MMF into the therapeutic armamentarium of LN and the extension of the use of the European intravenous cyclophosphamide guideline.

Availability of the patient's first renal biopsy specimen preserved for re-evaluation.

Availability of essential clinical data to carry out the study.

Signature of the informed consent by the patient.

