#### Sample size

For this proof-of-concept study, our objective is to analyze around **60 renal biopsy** samples (expandable according to the results obtained).

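### The objective is to predict response to the different LN drugs, but no analysis named in the plan estimates whether a marker's association with response differs by drug

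*Combined protocol and SAP*

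**What the plan says.** In the combined protocol and SAP, the Introduction states the purpose as "predicting the response (or lack thereof) to one or another therapy at the time of LN diagnosis", so that treatment decisions can be personalised. The objective at the end of that section is "to predict the renal response to the different drugs used in the treatment of LN".

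The Statistical Analysis section names these analyses:

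- A two-group comparison: "We will establish 2 groups of patients, according to the response to treatment and the clinical evolution of the patient with LN". The example given is complete remission, yes or no. The tests are chi-square or Fisher, t, and Mann-Whitney.
- A marker analysis: "The percentage of positive cells and staining intensity will be correlated with the different patterns of response to treatment and evolution of LN".
- Regression models, with one or several explanatory variables, to "explore the relationships between the different variables studied (clinical, histopathological, therapeutic", among others) and the renal outcomes, with significance at p < 0.05.
- An open clause: "We will carry out other different statistical methods according to the results that we observe from our initial analysis".

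The Methods section records which LN drugs each patient received (glucocorticoids, AZA, MMF, CYC, belimumab, rituximab) and for how long. The Sample size section plans about 60 biopsies in a proof-of-concept study and allows expansion. It gives no effect size, response rate, power or number per drug.

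**The concern.** Choosing between drugs requires knowing whether a marker's association with response is different under one drug than under another. A marker that goes with better or worse response whatever is given is prognostic: it is informative about the patient but does not help choose the drug. The named analyses estimate the second kind of association. Entering therapy as a covariate allows response rates to differ by drug but still yields one common marker effect.

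Two things are at stake. First, with p < 0.05 as the only criterion and no rule of interpretation, the final report could present a prognostic marker as predicting response to a drug. The Experimental Strategy section makes this a practical risk, because it selects BLYS and its receptors partly for their link with progression and severity. Second, a marker that matters under one drug only is diluted when all patients are analysed together and can be missed.

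**Working it through.** **1. Objective against analyses.**

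| Named analysis | What it estimates | Marker effect by drug? |
|---|---|---|
| Two outcome groups | Marker difference, responders v non-responders, all drugs | No |
| Staining correlated with response patterns | Overall association | No |
| Regression with therapeutic variables | Common marker effect, adjusted for therapy | Not unless a marker x drug term or within-drug fit is added; none is stated |
| Other methods | Unnamed, chosen after the first results | Not specified |

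The plan also gives no rule for assigning patients with combined or sequential therapy to a drug group.

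**2. The plan's own figure.** The target of about 60 cannot be reproduced, because no inputs are given for it.

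**3. What the all-patient comparison shows.** All inputs except n = 60 are assumptions: two regimens A and B, a normally distributed marker, 40% complete response at the mean marker value, odds ratios (OR) per SD of marker, and a two-sided 0.05 level. The all-patient test is a t-test of the marker by complete response. The interaction test is a Firth logistic model with marker, regimen, marker x regimen and one or two severity covariates. Each scenario has 2,000 runs; ranges cover the one- and two-covariate runs.

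| OR in A / B | Patients in A / B | All-patient test significant | Median all-patient OR | Interaction test significant |
|---|---|---|---|---|
| 2 / 2 (prognostic) | 30 / 30 | 65-67% | 2.0 | 4-5% |
| 3 / 1.5 | 30 / 30 | 68-69% | 2.0-2.1 | 15-17% |
| 3 / 1 | 45 / 15 | 73-74% | 2.1 | 33-34% |
| 3 / 1 | 30 / 30 | 39-40% | 1.6 | 40% |
| 1 / 3 | 45 / 15 | 13-14% | 1.26 | 26-28% |

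A hand check is the patient-weighted geometric mean of the two ORs: √(3 × 1.5) = 2.12; 3^0.75 = 2.28; √3 = 1.73; 3^0.25 = 1.32. The simulated values lie at or a little below these. The first three rows look alike in the all-patient analysis although only the first marker is purely prognostic. The last two rows show the dilution.

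As a measure of separating drug-specific from prognostic markers (AUC, 0.5 = coin toss), the all-patient OR scores 0.52 and the interaction estimate 0.65 for 3/1.5 v 2/2 at 30/30. For 3/1 v 2/2 at 45/15 the scores are 0.55 and 0.75. The gain is real but modest.

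**4. Opposite effects.** Suppose response is 30% (low marker) v 70% (high) under one drug and 70% v 30% under the other, in equal groups. Each marker half then averages (0.30 + 0.70)/2 = 0.50. The pooled chi-square test rejects in about 3.5% of 20,000 runs.

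**5. What a by-drug analysis can deliver at n = 60.** For a high/low marker, SE = √Σ 1/(n p(1−p)) over four cells, and power = Φ(|ln ratio of ORs|/SE − 1.96). Take 30% v 60% under one drug and 45% v 45% under the other, with 15 per cell:

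- SE = √(0.317 + 0.278 + 0.269 + 0.269) = 1.065
- ratio of ORs = 3.5, ln = 1.253
- power = Φ(1.253/1.065 − 1.96) = 22%
- N for 80% power = 60 × (2.802 × 1.065/1.253)² ≈ 340

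With 30% v 70% against 50% v 50%, power is 35% and N about 192.

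For a continuous marker, the simulated within-regimen 95% CIs (upper limit divided by lower) span 5- to 8-fold with 30 patients, 12- to 20-fold with 15 and 25- to 33-fold with 10.

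**6. Non-random treatment** (30/30). Severity was correlated with marker, regimen choice and response. When it is unmeasured, a within-regimen OR of 3 becomes 1.87-2.08 (CI coverage 83-87%) and an OR of 1 becomes 0.72-0.79. When measured and adjusted, the medians are 2.83-2.86 and 1.01-1.02. If severity acts under one drug only and the marker has no effect of its own, a false interaction appears in 7.5-12.4% of runs, and in 5.0% once severity x regimen is added.

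**The case against.** The strongest reply is that this is under-specification in an exploratory study, not a wrong analysis. Therapeutic variables are in the regression, further methods are allowed, and the sample is "samples (expandable according to the results obtained"). Much of that stands. A reader might infer that the plan rules out a by-drug model, or that the investigators will report all-patient associations as drug-specific. The documents support neither: the regression wording is open, and no sentence says how such findings will be labelled. What remains is that the analysis answering the stated objective is not named, and that methods chosen after seeing results do not fill that gap.

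A second reply is that limiting biopsies to 2000 onwards makes treatment uniform. The stated reason is "theoretical homogenization in the therapeutic management of LN with the introduction of MMF into the therapeutic armamentarium of LN", but the same sentence also names the European cyclophosphamide regimen. More than one regimen is therefore expected.

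A third reply is that about 60 patients cannot support by-drug analysis. This largely stands. Two clean regimens is a favourable assumption, and an OR of 3 per SD under one drug with none under the other is a large contrast. If 20% of patients are effectively under the other regimen through switching, interaction power at 3 v 1 falls from 40% to 16%. It would be wrong to infer that adding an interaction test settles the matter. The low precision is a reason to limit the claims; it does not supply the missing analysis.

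**Conclusion.** The concern holds in this form: the objective asks about response to the different drugs, and no named analysis estimates a marker effect that differs by drug. That rests on the text alone. As written, the plan supports prognostic conclusions.

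The sizes are illustrative. They depend on assumed response rates, odds ratios, two regimens and their split, none of which the documents give. Under those assumptions the all-patient comparison at n = 60 cannot separate a prognostic marker from a drug-specific one, and interaction power is about 15-40%. Low power is not universal: for the opposite effects in step 4 it would be 85% with an equal split. This should be fixed before analysis. It does not make the study's prognostic findings invalid.

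**What to change.** 1. **Reporting rule.** State in the Statistical Analysis section that markers associated with response in all patients together are reported as prognostic, not as predicting response to a particular drug. This covers every marker, including the cell-lineage markers, MCP-1 and NGAL.

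2. **Exploratory by-regimen estimates for BLYS, BAFF-R, BCMA and TACI**, the markers the protocol makes its focus. Classify patients by initial LN regimen after biopsy and flag combinations and switches. Report the marker-response association within each regimen and the marker x regimen term, with 95% CIs and no significance claims. Name one baseline severity variable in advance for adjustment (proteinuria, eGFR or NIH activity index) and use a penalised (Firth) fit. As sensitivity checks, repeat with severity x regimen added, and without the combination and switch patients.

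3. **Decision rule.** Fix the minimum regimen size in advance. From regimen counts alone, before any marker-outcome result is seen, decide whether by-regimen estimates are reported or the objective and conclusion are stated as prognostic and exploratory.

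**Cost.** SAP wording, one model term for four markers, and one derived field from the chart review already scheduled in months 7-12. No new samples or stains are needed.

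**Downsides.** At 40% response there are 0.40 × 60 = 24 responders for five parameters with two regimens (six with severity x regimen), so the CIs will be as wide as in step 5 and will often not separate the two kinds of marker. Adjusting for one severity variable reduces, but does not remove, the bias in step 6, and the conclusion becomes more modest.

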#### Methods:

The following **general variables** will be collected:

- demographic data: age, sex, ethnicity.
- clinical data on SLE:
  - diagnosis and chronological data: time of SLE diagnosis, time of LN diagnosis, time from SLE diagnosis to LN.
  - 1997 ACR SLE classification criteria,
  - activity: involvement of different organs and systems by SELENA-SLEDAI (10) at the time of LN diagnosis and at the time of the last evaluation of the patient (or death, if applicable).
  - damage: by item and by domain according to the Systemic Lupus International Collaborating Clinics Damage Index (SDI) (11) at the time of LN diagnosis and at the time of the last evaluation of the patient (or death, if applicable).
  - comorbidity: arterial hypertension, diabetes, dyslipemia, smoking habit, severe infections, neoplasms, etc. at the time of LN diagnosis and at the time of the last evaluation of the patient (or death, if applicable).
- laboratory data at the time of LN diagnosis and at the time of the last evaluation of the patient (or death, if applicable):
  - blood (general tests): acute phase reactants (erythrocyte sedimentation rate and C-reactive protein), full blood count, creatinin, glomerular filtration rate, blood urea nitrogen, liver function tests, lipid profile.

- blood (serological tests): complement (C3 and C4), levels of anti-dsDNA antibodies, antiphospholipid antibodies: anticardiolipin (Ig M and Ig G), anti-beta2GP-1 (Ig M and Ig G), lupus anticoagulant.
- urine: hematuria, piuria, proteinuria, casts.
- histopathological markers of renal biopsy:
  - histological class according to the 2003 ISN/RPS classification (9).
  - National Institutes of Health (NIH) activity index (12): score (maximum 24) and by item (endocapillary hypercellularity, neutrophils/karyorrhexis, hyaline deposits/wire loops, fibrinoid necrosis, cellular or fibrocellular crescents, interstitial inflammation).
  - National Institutes of Health (NIH) chronicity index (12): score (maximum 12) and by item (global glomerulosclerosis, fibrous crescents, tubular atrophy, interstitial fibrosis).
  - markers related to B lymphocytes which may include but is not limited to: CD19, CD20 and CD138.
  - markers related to BLYS (B lymphocyte stimulator) and its functional consequences which may include but is not limited to expression of BLYS and its receptors: BAFF-R, BCMA and TACI.

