## **EXPERIMENTAL STRATEGY AND RATIONALE**

In this project we will use renal biopsies from patients with LN. These samples, preserved in 10% formaldehyde and embedded in paraffin blocks by the corresponding Anatomic Pathology Services, correspond to patients with LN who underwent renal biopsies in the centers participating in the project.

BLYS (B lymphocyte stimulator) plays a key role in the pathophysiology of LN (14). Therefore, in this study we will focus on markers related to BLYS and its functional consequences. On the one hand, we will analyze among others the expression levels of BLYS and its receptors (BAFF-R, BCMA and TACI), since the expression levels of BLYS and its receptors are elevated in serum and renal biopsies of patients with LN and are associated with disease progression and severity (15-17).

On the other hand, because BLYS induces B cell survival (14), we will analyze the expression levels of different B cell markers such as CD19 and CD20 among others. Finally, we will analyze the plasma cell marker CD138, since plasma cell infiltration is associated with increased severity of lupus nephritis (18). We will analyze the expression levels of markers of other cell lineages such as CD3 for T cells and CD68 for macrophages.

We will also analyze at least 2 biomarkers whose urinary levels in patients with LN have been associated with a worse prognosis of LN: the chemokine MCP-1 (monocyte chemoattractant protein-1) and the enzyme NGAL (neutrophil gelatinase-associated lipocalin) (19).

The expression of these markers will be initially determined by immunohistochemical staining of renal biopsies, which are preserved in formaldehyde. The samples will be stained and analyzed mainly in the Anatomic Pathology Service of the “Complejo Hospitalario Universitario de Vigo” and in the laboratories of the “Instituto de Investigación Sanitaria Galicia Sur” (IISGS), although the different participating centers will participate in this work to the extent possible and cost-effective for the project. Different methods of quantification will be used in function of the stains of the different markers.

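### Student's equal-variance t test is named for two outcome-defined groups that may differ in size and spread; Welch's t test protects the 5% level at almost no cost

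*Combined protocol and SAP*

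**What the plan says.** All references are to the combined protocol and SAP.

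- **Groups.** The Statistical Analysis section forms two groups by response and clinical course ("i.e., complete remission yes/no"). No expected remission rate or group split is given.
- **Continuous variables.** The rule is "the t-Student test for normal continuous variables, and the Mann-Whitney U test for variables with non-normal distribution". Normality is the only criterion for choosing. No Welch version, variance check or method of judging normality is named.
- **Categorical variables.** The χ² "test for categorical variables or Fisher's exact test when the expected frequencies are small".
- **Staining.** A separate sentence covers it: "The percentage of positive cells and staining intensity will be correlated with the different patterns of response to treatment and evolution of LN". No method is named. The Experimental Strategy and Rationale section leaves the scale open: "Different methods of quantification will be used in function of the stains of the different markers".
- **Histology scores.** Under Methods, the NIH activity index is collected as "score (maximum 24) and by item", and the chronicity index likewise with its own maximum of 12. Ordered scores are not mentioned in the test rule.
- **Size and threshold.** The Sample size section states that "our objective is to analyze around 60 renal biopsy samples", with no effect size, SD or power. The significance threshold is p < 0.05; sidedness is not stated.

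**The concern.** Student's t test assumes that both groups share one variance. When sizes and spreads both differ, its standard error is wrong: too small if the smaller group is the more variable, too large if the larger group is.

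Here the groups are defined by outcome, with no randomisation or matching to balance them. One group holds the complete responders. The other combines partial responders and non-responders, as the response definitions under Methods imply. That second group is a mixture, so equal spread cannot be presumed.

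A normality check does not help, because normal data with unequal variances pass it and go to the pooled test. At stake is whether the 5% threshold means 5% for markers analysed this way. Depending on the pattern, the plan could produce extra false leads or miss real differences.

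**Working it through.** **Inputs from the documents.** N about 60; threshold 0.05 (two-sided assumed); two groups by complete remission; Student's t for normal variables. The sample size has no calculation behind it, so there is no figure to reproduce.

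**Inputs assumed.** Group split from 30:30 to 15:45. SD ratio (smaller group divided by larger group) of 0.5, 1, 1.5 and 2. Normal data.

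**Step 1: why the error arises.** The true variance of the difference in means is σ₁²/n₁ + σ₂²/n₂. Student's t estimates it, on average, as σₚ²(1/n₁ + 1/n₂), where σₚ² = [(n₁−1)σ₁² + (n₂−1)σ₂²]/(n₁+n₂−2). The nominal critical value with 58 degrees of freedom is 2.002. Its effective value is 2.002 × √(estimated/true).

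- *20:40, smaller group SD 2, larger SD 1.* True: 4/20 + 1/40 = 0.225. Pooled: (19×4 + 39×1)/58 = 1.983, and 1.983 × 0.075 = 0.1487. Ratio 0.661, square root 0.813, effective critical value 1.627. Two-sided normal tail: about 10%.
- *15:45, same SDs.* True: 4/15 + 1/45 = 0.2889. Pooled: (14×4 + 44×1)/58 = 1.724, and 1.724 × 0.0889 = 0.1533. Ratio 0.531, square root 0.728, effective critical value 1.458. Tail: about 14%.
- *20:40, smaller group SD 1, larger SD 2.* True: 1/20 + 4/40 = 0.150. Pooled: (19×1 + 39×4)/58 = 3.017, and 3.017 × 0.075 = 0.2263. Ratio 1.509, square root 1.228, effective critical value 2.459. Tail: about 1.4%.

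With equal sizes or equal SDs the two expressions agree and there is essentially no distortion.

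**Step 2: simulation.** 40,000 datasets per row, equal means, N = 60. The normal tail in step 1 is a slight understatement.

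| Split | SD ratio (smaller/larger group) | Student | Welch |
|---|---|---|---|
| 30:30 | 2 | 5.1% | 5.0% |
| 20:40 | 1 | 5.1% | 5.0% |
| 24:36 | 1.5 | 6.9% | 5.0% |
| 24:36 | 2 | 8.4% | 5.0% |
| 20:40 | 1.5 | 8.5% | 5.1% |
| 20:40 | 2 | 11.2% | 5.1% |
| 15:45 | 1.5 | 10.7% | 5.0% |
| 15:45 | 2 | 15.5% | 5.2% |
| 20:40 | 0.5 | 1.7% | 4.8% |
| 15:45 | 0.5 | 0.9% | 5.0% |

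A separate run gave 11.5% and 15.3% for 20:40 and 15:45 at ratio 2, the same within a few tenths of a point.

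**Step 3: power in the reverse pattern.** At 20:40, with SD 1 in the smaller group, SD 2 in the larger and a true difference of 1 unit, power is 55% for Student and 72% for Welch.

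**Step 4: cost of Welch.** With normal data, equal variances and unequal groups, Welch loses about 1–2 percentage points of power.

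**Step 5: ordered scores.** The plan names no test for them, so any loss depends on how it is read. If an analyst chose χ² for a four-level score (assumed even base distribution, proportional odds ratio 3), power would be 41% against 59% for Mann-Whitney at 20:40, and 46% against 63% at 30:30. If the analyst chose Mann-Whitney, there would be no loss.

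**The case against.** **The inflation is conditional.** This stands. It needs both clear imbalance and a larger SD in the smaller group. A reader might infer that false-positive rates will double or triple. The documents do not support that, because they give neither split nor SDs. Doubling needs roughly 1:2 with SD ratio 2, or 1:3 with ratio 1.5. Tripling needs roughly 1:3 with ratio 2. At 24:36 with ratios up to 2 the rate never doubles.

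**The plan does not send ordered scores to χ².** This also stands. A reader might infer it from the categorical and continuous labels. But the Mann-Whitney clause covers variables with a non-normal distribution generally, and NIH scores fit there naturally. Staining intensity has its own sentence about correlation, and its scale is not fixed. What remains is an unstated choice.

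**Welch is not right for everything.** It would be tempting to prescribe it for all continuous variables. For skewed markers that would do harm: with simulated lognormal data at 20:40 (log-SD 1, shift 0.8 on the log scale, smaller group higher), power was 51% for Welch and 80% for Mann-Whitney. The existing Mann-Whitney route should stay. It is not exact under unequal spread either (8.7% at 20:40, ratio 2, normal data).

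**The wording may be generic, and the study is exploratory.** The test's name may mean any two-sample t test, although the literal reading is the pooled one. This is a proof-of-concept study that also plans logistic regression, so these tests are not the only route by which a marker is judged. Both points lower the severity. Neither is a reason to leave the pooled test in place.

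**Conclusion.** The point holds as a minor improvement. For variables treated as normal, the plan names a test whose error rate depends on an equality of spread that an outcome-defined comparison cannot guarantee. A near-free alternative does not need that equality.

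At N = 60 the Student error rate is 5% if sizes or SDs are equal. It is about 7–8% at 24:36 with the smaller group's SD 1.5–2 times larger, about 11% at 20:40 and 15% at 15:45 with ratio 2, and about 1.7% at 20:40 with the ratio reversed. Welch stays near 5% in all of these. The figures rest on assumed splits, assumed SD ratios and normal data; they show the range of possible distortion and do not forecast it for this study.

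The handling of ordered scores is an unspecified detail, not an error.

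**What to change.** In the Statistical Analysis section:

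1. Name Welch's t test in place of Student's for continuous variables treated as normal.
2. Keep Mann-Whitney for non-normal variables.
3. Report each group difference with its 95% confidence interval beside the p value.
4. As a clarification, state that ordered scores (NIH items and any graded staining intensity) are compared by Mann-Whitney with a tie correction or by a trend test, leaving χ² and Fisher for unordered categories.

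This takes about two sentences and no new data or patients, and the methods are standard in statistical software. The one statistical cost is the 1–2 power points noted above, when variances are truly equal and groups unequal.

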**Variables will be collected to establish different patterns of response to treatment and evolution of LN:**

- a) complete renal response, defined according to EULAR/ERA-EDTA recommendations (13): proteinuria  $<0.5$  g/24 hours and (near) normal estimated GFR.
- b) partial renal response, defined according to EULAR/ERA-EDTA recommendations (13):  $\geq 50\%$  proteinuria reduction to subnephrotic levels and (near) normal eGFR
- c) no response: all the other cases.
- d) proteinuria levels at 12 months of treatment,
- e) renal relapse as defined as reproducible increase in uPCR to  $>1$  g if the baseline value was  $<0.2$  g, to  $>2$  g if the baseline value was between  $0.2$  g and  $1$  g, or more than twice the value at baseline if the baseline value was  $>1$  g AND/OR reproducible decrease in GFR of  $>20\%$ , accompanied by proteinuria ( $>1$  g), and/or RBC and/or WBC cellular casts (yes/no and number of flares), e) time to first flare, f) chronic renal failure,
- f) end-stage renal disease requiring dialysis and/or renal transplantation.

Data collection will be based on the clinical history of the patients included in the study.

Confidentiality will be respected in accordance with RD 1720/2007 and the Data Protection Laws. Approval will be requested from the **Galician Clinical Research Ethics Committee (CEIC)** as well as from the CEIC of each center, if necessary.

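### One unqualified p<0.05 rule covers 11 named tissue markers and about six renal outcomes with no lead comparison, and the results-driven enlargement of the sample has no stated rule

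*Combined protocol and SAP*

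**What the plan says.** - **Significance rule (Statistical Analysis).** Staining results are the predictors: "The percentage of positive cells and staining intensity will be correlated with the different patterns of response to treatment and evolution of LN". Regressions (univariate and multivariate) follow, "to explore the relationships between the different variables studied" and the renal outcomes. The next sentence states that p-values below 0.05 "will be considered significant". No primary outcome, lead marker or multiplicity method is named.
- **Markers (Methods; Experimental Strategy and Rationale).** Eleven are named: BLYS, BAFF-R, BCMA, TACI, CD19, CD20, CD138, CD3, CD68, MCP-1 and NGAL. The lists are explicitly open, and "Different methods of quantification will be used in function of the stains of the different markers".
- **Outcomes (Methods, list of response patterns).** Response category (complete, partial, none), proteinuria at 12 months, relapse, "time to first flare", chronic renal failure and end-stage renal disease.
- **Partial priorities.** Patients are split into two groups ("i.e., complete remission yes/no"), and the rationale says that "in this study we will focus on markers related to BLYS and its functional consequences". Neither is called primary.
- **Results-driven steps.** "We will carry out other different statistical methods according to the results that we observe from our initial analysis". The Sample Size section describes a proof-of-concept study of about 60 biopsies that may be enlarged depending on results. Timelines schedules one statistical analysis, in month 16.

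**The concern.** The study exists to pick out biopsy markers worth pursuing as predictors of renal response. Under the plan as written, a BLYS-related marker tested against complete remission and a late-added marker tested against relapse carry the same label if both fall below 0.05. A reader of the final report could not tell a comparison chosen beforehand from the best of many, nor know how many were tried. With dozens of tests, some chance hits are to be expected, and each would be declared significant under the plan's own rule.

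Enlargement adds a second uncertainty. If more biopsies are added because of outcome results, the error rate depends on whether old and new data are pooled and retested. The plan does not say.

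**Working it through.** **Inputs from the documents.** Threshold 0.05 (sidedness not stated; taken as two-sided). Markers: 4 BLYS-related + 3 B-cell or plasma-cell + 2 other lineages + 2 known from urine studies = 11. Readouts per marker: 2. Outcomes: 6, counting response category as one. Sample: about 60. The plan gives no effect size, variance, response rate or power for the 60, so there is no figure of its own to reproduce.

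**Assumptions.** Correlation between tests, group split, effect sizes, number of true markers and enlarged sample sizes are mine; the documents give none.

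**1. Number of tests and expected false positives, all nulls true** (0.05 × number of tests, whatever the correlation):
- complete remission only, one readout: 11 tests, 0.05 × 11 = 0.55
- six outcomes, one readout: 11 × 6 = 66 tests, 0.05 × 66 = 3.3
- six outcomes, both readouts: 66 × 2 = 132 tests, 0.05 × 132 = 6.6

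These counts leave out the clinical, laboratory and treatment variables that enter the same analyses.

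**2. Chance of at least one significant marker for complete remission, 11 null markers, one readout.** Independent: 1 − 0.95^11 = 0.431. Equicorrelated normal test statistics: 0.304 at correlation 0.5 and 0.180 at 0.8. For the four BLYS-related markers alone, independent: 1 − 0.95^4 = 0.185.

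**3. What Benjamini-Hochberg (BH) at 10% would do as the decision rule.** With all 11 null, the chance of any false declaration falls to 10%, 8% and 6% at correlations 0, 0.5 and 0.8. With one true marker among 11 and a 30/30 split (simulation, normal approximation; each cell is unadjusted → BH):

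| Effect, correlation | Power | False share of all declarations over repeated studies | Mean per-study false discovery proportion |
|---|---|---|---|
| 0.8 SD, 0 | 87% → 70% | 36% → 21% | 24% → 9% |
| 0.5 SD, 0 | 49% → 27% | 50% → 35% | 31% → 9% |
| 0.8 SD, 0.8 | 87% → 69% | 37% → 36% | 14% → 6% |
| 0.5 SD, 0.8 | 49% → 25% | 50% → 59% | 14% → 6% |

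The last column counts a study with no declaration as zero. In a four-marker family with one true marker (independent), power goes from 87% to 81% at 0.8 SD and from 49% to 40% at 0.5 SD. The false share at 0.8 SD is 15% unadjusted and 16% with BH, so there the gain comes from the smaller family.

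**4. Enlargement, as an example under an assumed rule.** Test once at 60; if not significant, enlarge to 120, pool and retest at 0.05. The two statistics have correlation √(60/120) = 0.707, and the type I error of a single test is 8.3%. A common nominal p of about 0.029 at both looks would hold it at 5%.

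**The case against.** The strongest reply is that this is openly a screening study. It is called proof-of-concept, and the word explore stands in the sentence directly before the significance rule. In such a study a missed marker may cost more than a false lead. The rationale also gives literature grounds for most markers, so one true marker among 11 may be too pessimistic: with three true at 0.8 SD (independent), the false share is only 13% unadjusted and 10% with BH. Correlated markers are plausible, because the rationale itself links the B-cell markers to BLYS signalling. At correlation 0.8 BH costs power without lowering the false share.

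Much of this stands. It rules out insisting on strict familywise control or on BH as the only decision rule. It does not remove the core point, because neither the exploratory wording nor the two partial priorities qualifies the rule by which a result is declared.

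A reader might infer two stronger things that the documents do not support:
- **That the plan presents itself as confirmatory.** It does not; the exploratory intent is visible, only not carried into the rule.
- **That the plan will pool and retest after enlargement.** Timelines shows a single analysis. The results that prompt enlargement could also be laboratory findings such as staining yield, since laboratory work runs in months 7-12, before the analysis. A pooled retest is possible under the text but not planned in it.

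**Conclusion.** The point holds. One unadjusted threshold applies to at least 66 marker-outcome comparisons (132 with both readouts) with no lead among them. For complete remission alone, the chance of at least one false marker is 43%, 30% or 18% at correlation 0, 0.5 or 0.8, if all 11 are null and one readout is used. The expected 3.3 false positives in 66 tests needs only that all nulls are true.

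The test counts and the missing enlargement rule rest on the text alone. The power and false-share figures rest on assumed effects, splits and correlations, and show that BH as the sole rule is a trade-off. The 8.3% for a retest is an illustration under one assumed rule, not a property of the plan.

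This should be changed before markers are linked to outcomes, but it does not invalidate the study. Whether pooled-treatment comparisons can serve the drug-specific objective in the Introduction is a separate matter; this point does not ask for that objective to be downgraded.

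**What to change.** 1. **Name a lead comparison.** In Statistical Analysis, make complete renal response yes/no (the existing two-group split), at one stated time point, the lead. Before linkage to outcomes, fix the marker family (the BLYS-related markers or all 11) and one lead readout per marker; still report the second readout. For that family, show unadjusted and BH-adjusted p-values side by side and state the number of tests. BH as the sole decision rule is optional.
2. **Relabel the rest.** For all other markers, readouts, outcomes, regressions and results-driven methods, replace the blanket significance label with hypothesis-generating, and report estimates with 95% confidence intervals.
3. **State the enlargement rule.** Say what triggers it. If outcome results do, report the initial set of about 60 as its own analysis. Analyse added biopsies separately or under a pre-stated adjusted threshold, and do not pool and retest at an unadjusted 0.05.

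**Cost.** For the initial set this is analysis wording, with no new patients or assays. Fewer results may be called significant. Keeping unadjusted values in view avoids imposing the BH power loss shown above; a sponsor who adopts BH as the decision rule accepts it.
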